10.2 Selection of Study Design

This study has been designed based on the draft FDA Guidance for Industry; Estrogen and Estrogen/Progestin Drug Products to Treat Vasomotor Symptoms and VVA (January 2003) and the Draft FDA Guidance on Estradiol Vaginal Cream (revised September 2014).^{12,13} Statistical analyses of the clinical data will be based on recommendations in the FDA Guidances.^{12-16,18}

10.3 Selection of Study Population

10.3.1 Inclusion Criteria

1. Signed IRB-approved ICF that meets all criteria of current FDA regulations.
2. Postmenopausal females aged 30-75 years inclusive. Postmenopausal is defined as follows:
 - a. At least 6 months of spontaneous amenorrhea.
 - b. At least 6 weeks post-surgical bilateral oophorectomy, with or without hysterectomy.
 - c. Hysterectomy without oophorectomy if of age that the Investigator believes would have naturally reached 12 months of spontaneous amenorrhea if uterus had remained intact.
3. Patients with a serum Follicle Stimulating Hormone (FSH) level of ≥ 40 mIU/mL at Screening.
4. Have $\leq 5\%$ superficial cells on vaginal smear cytology.
5. Have a vaginal pH > 5.0 .
6. At least one of the following patient self-assessed moderate to severe symptoms of VVA from the following list that is identified by the patient as being most bothersome to her:

CONFIDENTIAL PROTOCOL

A Randomized, Double-Blind, Placebo-Controlled, Parallel-Design, Multiple-Site Study to Evaluate the Therapeutic Equivalence of Estradiol Vaginal Cream, USP, 0.01% (Prasco LLC) to Estrace[®] Cream (Estradiol Vaginal Cream, USP, 0.01%) (Warner Chilcott) in the Treatment of Vulvar and Vaginal Atrophy, 71759501

- Vaginal Dryness
- Vaginal and/or Vulvar Irritation/Itching
- Dysuria
- Vaginal Pain associated with sexual activity
- Vaginal Bleeding associated with sexual activity (presence or absence)

*Provided that patient is currently sexually active and plans to remain so throughout study.

7. Have “Normal” Screening mammogram completed within 9 months before Screening in all patients > 40 years old, with no findings that, in the opinion of the Investigator, would indicate any suspicion of breast malignancy.
8. Normal clinical breast examination at Screening.
9. Patients with an intact uterus (including patients who underwent a partial hysterectomy) must have a documented papanicolaou (PAP) smear conducted within the previous 12 months with no findings that the Investigator believes would contraindicate the use of topical vaginal estradiol.
10. Patients with an intact uterus should have vaginal ultrasonography results within 3 months before Screening to confirm an inactive endometrial lining, defined as endometrial thickness < 4 mm.

10.3.2 Exclusion Criteria

1. Significant history or current evidence of chronic infectious disease, system disorder, organ disorder or other medical condition that in the Investigator’s opinion would place the study patient at undue risk by participation or could jeopardize the integrity of the study evaluations.
2. Any clinically significant laboratory finding that, in the Investigator’s opinion, would contraindicate the use of estradiol or compromise patient safety.
3. Patients with known concurrent vaginal infections including but not limited to: *Candida albicans*, *Trichomonas vaginalis*, *Chlamydia trachomatis*, *Neisseria gonorrhoea* or *Gardherella vaginalis*.
4. Patients with active vaginal herpes simplex infection or have had an outbreak within 30 days before the Screening.
5. Patients with known, suspected or current history of carcinoma of the breast.
6. Patients with baseline systolic blood pressure of > 150 mmHg and/or diastolic pressure > 90 mmHg.

CONFIDENTIAL PROTOCOL

A Randomized, Double-Blind, Placebo-Controlled, Parallel-Design, Multiple-Site Study to Evaluate the
Therapeutic Equivalence of Estradiol Vaginal Cream, USP, 0.01% (Prasco LLC) to Estrace®
Cream (Estradiol Vaginal Cream, USP, 0.01%) (Warner Chilcott) in the Treatment of Vulvar and Vaginal
Atrophy, 71759501

7. Any patient with past or current undiagnosed vaginal bleeding or significant risk factors for endometrial cancer.
8. Any history of estrogen-dependent neoplasia (e.g., endometrial cancer).
9. Patients with known, suspected or current history of hormone dependent tumor.
10. History of acute thrombophlebitis or thromboembolic disorder.
11. Any prescription treatment for vaginal dryness/irritation within 14 days before Screening or any OTC or natural remedies within 7 days before Screening.
12. Any prescription treatment for bacterial or yeast infections within 30 days before Screening.
13. Fasting triglyceride levels > 350 mg/dL.
14. History of radiation therapy or recent (within previous 6 weeks) surgical therapy to the vaginal or cervical areas.
15. Any known or suspected allergies that, in the Investigator's opinion, would compromise the safety of the patient.
16. Patients who have used vaginal hormonal products (rings, creams, gels) within the 7 days before Screening.
17. Patients who have used transdermal estrogen and/or progestin therapy within the 28 days before Screening.
18. Patients who have used oral estrogen and/ or progestin therapy or intrauterine progestin therapy within the 56 days before Screening.
19. Patients who have used progestin implants or estrogen alone injectable drug therapy within the 3 months before Screening.
20. Patients who have used estrogen pellet therapy or progestin injectable drug therapy within 6 months before Screening.
21. History of significant alcohol abuse within 1 year prior to Screening or regular use of alcohol within 6 months before Screening (more than 14 units of alcohol per week [1 unit = 150 mL of wine, 360 mL of beer, or 45 mL of 40% alcohol]).
22. History of significant drug abuse within 1 year prior to Screening, use of soft drugs (such as marijuana) within 3 months before Screening, or hard drugs (such as cocaine, phencyclidine [PCP], crack, opioid derivatives including heroin, and amphetamine derivatives) within 1 year before screening.
23. Use within 30 days of Screening with known strong CYP3A4 inducers or inhibitors that, in the opinion if the Investigator, may affect estrogen metabolism. Examples of strong CYP3A4 inhibitors are macrolide antibiotics such as clarithromycin and telithromycin; azole antifungals such as itraconazole and ketoconazole; antidepressants such as

CONFIDENTIAL PROTOCOL

A Randomized, Double-Blind, Placebo-Controlled, Parallel-Design, Multiple-Site Study to Evaluate the Therapeutic Equivalence of Estradiol Vaginal Cream, USP, 0.01% (Prasco LLC) to Estrace[®] Cream (Estradiol Vaginal Cream, USP, 0.01%) (Warner Chilcott) in the Treatment of Vulvar and Vaginal Atrophy, 71759501

nefazodone; and foods such as grapefruit or grapefruit juice. Examples of strong CYP3A4 inducers are anticonvulsants such carbamazepine and phenytoin; bactericidals such as rifampin and rifabutin; and natural health products such as St John's wort.

24. Inability to understand the requirements of the study and the relative information or are unable or not willing to comply with the study protocol.
25. Receipt of any drug as part of a research study within 30 days before Screening.
26. Employees of the Investigator or research center or their immediate family members.
27. Patients who have participated in this study previously.

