14.0 APPENDICES

14.1 APPENDIX A: Clinical Laboratory Testing

CLINICAL LABORATORY TESTING

As part of the Screening Procedures the blood and cytology samples will be obtained for the following laboratory evaluations:

Serum FSH

Fasting Triglycerides

Vaginal Cytology

PAP Smear (as appropriate)

All samples will be sent to the central laboratory:

CONFIDENTIAL PROTOCOL

A Randomized, Double-Blind, Placebo-Controlled, Parallel-Design, Multiple-Site Study to Evaluate the Therapeutic Equivalence of Estradiol Vaginal Cream, USP, 0.01% (Prasco LLC) to Estrace[®] Cream (Estradiol Vaginal Cream, USP, 0.01%) (Warner Chilcott) in the Treatment of Vulvar and Vaginal Atrophy, 71759501

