The WHIMS estrogen plus progestin ancillary study of WHI enrolled 4,532 predominantly healthy postmenopausal women 65 years of age and older (47 percent were 65 to 69 years of age; 35 percent were 70 to 74 years; 18 percent were 75 years of age and older) to evaluate the effects of daily CE (0.625 mg) plus MPA (2.5 mg) on the incidence of probable dementia (primary outcome) compared to placebo.

After an average follow-up of 4 years, the relative risk of probable dementia for CE plus MPA versus placebo was 2.05 (95 percent CI, 1.21-3.48). The absolute risk of probable dementia for CE plus MPA versus placebo was 45 versus 22 per 10,000 women-years. Probable dementia as defined in this study included AD, VaD and mixed types (having features of both AD and VaD). The most common classification of probable dementia in the treatment group and the placebo group was AD. Since the ancillary study was conducted in women 65 to 79 years of age, it is unknown whether these findings apply to younger postmenopausal women [see **WARNINGS, Probable Dementia and PRECAUTIONS, Geriatric Use**].

When data from the two populations were pooled as planned in the WHIMS protocol, the reported overall relative risk for probable dementia was 1.76 (95 percent CI, 1.19-2.60). Differences between groups became apparent in the first year of treatment. It is unknown whether these findings apply to younger postmenopausal women [see **WARNINGS, Probable Dementia and PRECAUTIONS, Geriatric Use**].

INDICATIONS AND USAGE

ESTRACE (estradiol vaginal cream, USP, 0.01%) is indicated in the treatment of moderate to severe symptoms of vulvar and vaginal atrophy due to menopause.

CONTRAINdications

ESTRACE (estradiol vaginal cream, USP, 0.01%) should not be used in women with any of the following conditions:

1. Undiagnosed abnormal genital bleeding.
2. Known, suspected, or history of cancer of the breast.
3. Known or suspected estrogen-dependent neoplasia.
4. Active DVT, PE or history of these conditions.
5. Active arterial thromboembolic disease (for example, stroke, MI) or a history of these conditions.
6. Known anaphylactic reaction or angioedema to ESTRACE (estradiol vaginal cream, USP, 0.01%).
7. Known liver dysfunction or disease.
8. Known protein C, protein S, or antithrombin deficiency, or other known thrombophilic disorders.
9. Known or suspected pregnancy.

WARNINGS

See **BOXED WARNINGS**.

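### Known liver disease and known thrombophilia are contraindications in the bound-in label, but no eligibility criterion names them and their exclusion rests mainly on Investigator judgement

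*Protocol*

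**What the plan says.** Appendix C of the protocol is the Estrace product insert. Its Contraindications section says that the product "should not be used in women with any of the following conditions" and then numbers nine. Item 7 is "Known liver dysfunction or disease". Item 8 is "Known protein C, protein S, or antithrombin deficiency, or other known thrombophilic disorders". Neither carries a severity threshold or leaves the matter to the prescriber's opinion.

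Protocol 10.3.2 has 27 exclusion criteria, repeated in the Synopsis. Four bear on this point:

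- Criterion 1 covers significant history or current evidence of a system disorder, organ disorder or other condition, if the Investigator believes that it "would place the study patient at undue risk by participation or could jeopardize the integrity of the study evaluations".
- Criterion 2 covers a clinically significant laboratory finding that, in the Investigator's view, "would contraindicate the use of estradiol or compromise patient safety".
- Criterion 10 reads "History of acute thrombophlebitis or thromboembolic disorder" and has no opinion qualifier.
- Criterion 15 covers allergies that, in the Investigator's view, "would compromise the safety of the patient".

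Appendix A introduces the screening panel with the words "As part of the Screening Procedures the blood and cytology samples will be obtained for the following laboratory evaluations" and lists FSH, fasting triglycerides, vaginal cytology and, where appropriate, a PAP smear. Section 10.6.2 has the site take acute and chronic medical history at Visit 1. Section 10.7.1 gives Appendix C the role of Reference Safety Information for judging expectedness. No text makes its contraindications entry criteria.

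**The concern.** This is a question of patient safety. The label states items 7 and 8 flatly. The protocol reaches liver disease, and on a narrow reading thrombophilia, only after an Investigator has decided that the history is significant and the risk undue. A site that does not reach that view can randomise the woman and still comply with 10.3.2, and two sites can decide differently on the same history.

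The label gives reasons to care. It warns that systemic absorption may occur with this cream, describes the liver as the main place where estrogens are transformed, and cautions that estrogens may be metabolized poorly when liver function is impaired. Deep vein thrombosis is in the boxed warning. The patient leaflet tells women with present or past liver problems not to start.

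The drafting is also uneven. Raised triglycerides and raised blood pressure are only Precautions in the label, yet the protocol gives them fixed limits (above 350 mg/dL in criterion 13; above 150 mmHg systolic or 90 mmHg diastolic in criterion 6). Two outright contraindications get no line of their own. None of the study objectives needs these women.

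**Working it through.** There is no figure in the plan to reproduce. The check sets the nine contraindications of Appendix C against the inclusion criteria (10.3.1), the exclusion criteria (10.3.2) and the study procedures (10.6).

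| Contraindication (Appendix C) | Where the protocol handles it | Opinion needed? |
|---|---|---|
| 1. Undiagnosed genital bleeding | Exclusion 7 | No |
| 2. Breast cancer | Exclusion 5 | No |
| 3. Estrogen-dependent neoplasia | Exclusions 8 and 9 | No |
| 4. DVT or PE | Exclusion 10 | No |
| 5. Arterial thromboembolic disease (stroke, MI) | Exclusion 10, only if read broadly; neither is named | No, on that reading |
| 6. Anaphylaxis or angioedema to the product | Exclusion 15 | Yes |
| 7. Liver disease | Not named; exclusions 1 and 2 only | Yes |
| 8. Thrombophilia | Not named; exclusions 1 and 2, or 10 if read broadly | Yes, unless 10 is read broadly |
| 9. Pregnancy | Inclusions 2 and 3 (postmenopausal, FSH) and the negative-test rule in 10.6.13 | No |

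**What does not depend on reading.** Items 7 and 8 are the two conditions that no criterion or procedure names or addresses specifically.

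**What does.** The number of items resting only on criteria 1 and 2 turns on criterion 10:

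- Broad reading, which takes in arterial disease and a clotting tendency without an event: items 5 and 8 are covered, leaving item 7, so 1.
- Narrow reading, which takes in neither: items 5, 7 and 8 are left, so 3.
- Mixed reading, with stroke and MI inside criterion 10 but thrombophilia without an event outside it: items 7 and 8 are left, so 2.

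Liver disease is in the group on every reading. Item 6 stands apart: it has its own criterion, but an opinion-qualified one.

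**How far criterion 2 reaches.** It needs a laboratory finding. Of the 4 evaluations in Appendix A, 0 are liver or clotting tests, so for these two conditions criterion 2 can act only on a result from outside the study. Criterion 1 carries the weight.

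**Context only.** Allocation is 2:2:1, so a randomised woman has a (2 + 2)/5 = 80% chance of an active cream. The dose is 2 g × 0.1 mg/g = 0.2 mg estradiol a day, or 0.2 × 7 = 1.4 mg over the study. The 2 g dose is the lower end of the labelled initial range of 2 to 4 g, so the study dose lies within the use to which the contraindications apply. None of these figures measures harm, and nor does the laboratory count.

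**The case against.** The strongest reply is that criterion 1 already does the job. Liver disease is an organ disorder, and thrombophilia is at least another medical condition. The contraindication list is bound into the same document, history and a physical exam are taken at Visit 1, eligibility is reviewed at Visits 1 and 2, and section 12.1 sends the package insert to the IRB as applicable. For harm to arise, an Investigator would have to know of the condition, have the label to hand and still accept the risk. This largely stands as a statement about likely practice, but it does not make the exclusion mandatory or uniform.

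Second, criterion 10 speaks of a disorder, not an event, so it may be unfair to read it widely for stroke and narrowly for thrombophilia. This stands. A reader might infer that exactly two of nine contraindications have no other route; the documents do not support that count as a fixed quantity, since it is 1, 2 or 3 depending on the reading.

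Third, exposure is seven days at the lowest labelled initial dose, and the liver caution in the label carries no risk estimate for such use. This stands too. The label, however, makes no exception for short use.

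Fourth, the FDA guidances cited in 10.2 and the Case Report Form booklet cited in SAP section 1 are not available here. The forms may prompt for these conditions, so nothing firm can be said about site practice.

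**Conclusion.** The point holds as a gap in the eligibility wording. Liver disease is excluded only by Investigator judgement, whichever way the other criteria are read. Known thrombophilia without an event is in the same position unless criterion 10 is read broadly, and stroke and MI rely on that same reading.

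A reader might go further and infer that the protocol breaches its own rules, or that it sets out to enrol contraindicated women. Neither follows. Appendix C serves formally as Reference Safety Information, and no text binds eligibility to its contraindications. Most Investigators would probably exclude these women under criterion 1. The documents give no prevalence, so the number at risk is unknown and may be very small. The endpoint, power and type I error are untouched.

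This is a cheap improvement in patient safety that should be made, not a breach. Confidence is high in the textual mapping and much lower in any practical consequence.

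**What to change.** In 10.3.2 and the Synopsis, add one mandatory exclusion, free of any opinion qualifier, that names known liver disease or impaired liver function, any known thrombophilic disorder, and any other condition in the Contraindications section of Appendix C. The closing clause also makes item 6 mandatory and settles the doubt about item 5. Check it against the medical history already taken at Visit 1. No new test is needed, because the label words both missing items as known conditions. If the sponsor means to leave these women eligible, the protocol should say why.

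The cost is one line in the criteria and in the screening checklist, plus an unquantified number of extra screen failures. Because the label sets no severity threshold for liver disease, Investigators would also lose discretion over mild liver diagnoses.

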10.3.3 Restrictions During the Study

Patients will be instructed to refrain from the following throughout the study:

- Any kind of estrogen, progesterone or androgen hormone replacement.
- Any other treatments, prescription, OTC or natural products or natural methods, for the treatment of vaginal dryness/irritation including but not limited to vaginal lubricants, oils, creams, jellies, food products or saliva.
- Any vaginal drug products other than the study product (e.g., vaginal anti-fungals).
- Use within 30 days of Screening with known strong CYP3A4 inducers or inhibitors that, in the opinion if the Investigator, may affect estrogen metabolism. Examples of strong CYP3A4 inhibitors are macrolide antibiotics such as clarithromycin and telithromycin; azole antifungals such as itraconazole and ketoconazole; antidepressants such as nefazodone; and foods such as grapefruit or grapefruit juice. Examples of strong CYP3A4 inducers are anticonvulsants such carbamazepine and phenytoin; bactericidals such as rifampin and rifabutin; and natural health products such as St John's wort.

10.3.4 Removal of Patients from the Study

Patients will be advised that they are free to withdraw from the study at any time for any reason or, if necessary, the Investigator or Sponsor may withdraw a patient from the study to protect the health of that patient. A patient may also be withdrawn for not complying with study procedures. Patients who withdraw or are withdrawn from the study will not be replaced. The clinical report will include all reasons for early withdrawals.

Reasons for early termination may include, but are not limited to the following:

- Patient withdrew consent.
- Significant adverse event (AE) that led the Investigator/Sponsor or patient to withdraw for safety reasons.
- Non-compliance with protocol requirements (e.g., use of restricted medication, not following dosing procedures, failure to make scheduled study visits in a timely fashion).

CONFIDENTIAL PROTOCOL

A Randomized, Double-Blind, Placebo-Controlled, Parallel-Design, Multiple-Site Study to Evaluate the Therapeutic Equivalence of Estradiol Vaginal Cream, USP, 0.01% (Prasco LLC) to Estrace[®] Cream (Estradiol Vaginal Cream, USP, 0.01%) (Warner Chilcott) in the Treatment of Vulvar and Vaginal Atrophy, 71759501

- Pregnancy.
- Significant worsening of VVA such that the Investigator/Sponsor and/or patient believe it is in the best interest of the patient to withdraw from the study and be provided alternative treatment.
- Participant enrolls in another clinical trial, or is found to have previously enrolled in this clinical trial.

10.3.5 Early Terminations

If a patient terminates from the study early after being randomized, all efforts will be made to complete the patient's next visit study procedures. For early termination, Visit 3 (Day 8 or Day 9) End of Study or Early Termination (See Section 6.0) shall be completed and the Investigator shall fully document the reason for early termination.

10.4 Treatments

10.4.1 Treatment Administration

At Visit 2, following a 28-day screening period, eligible patients will be provided with 1 x 42.5 gram tube of study product along with verbal and written instructions on its administration. Patients will be required to self-administer 2 grams of study product once daily at approximately the same time of the day, for seven consecutive days. The last dose should be applied on the day before Visit 3. Patients should not dose on the day of Visit 3.

Patients will gently squeeze the cream out of the tube and into the applicator until the required amount (2 grams) is filled based on the calibrated markings on the applicator. The applicator is then to be unscrewed from the tube and cap replaced on the tube. To deliver study product, patients are to lie on back and insert the applicator into the vagina and deliver the dose by pressing down on the plunger. The applicator is to be cleaned with mild soap and warm water after each application.

Based on an approximate 2 grams application per day, 1 x 42.5 gram tube of cream should be sufficient to last for the full treatment period of the study (seven days). Patients will begin dosing on the day of Visit 2 (i.e., Day 1).

10.4.2 Identity of Investigational Product

The following products will be used in the study:

- **Test:** Estradiol Vaginal Cream USP, 0.01% (Prasco LLC)
- **Reference:** Estrace[®] Cream (Estradiol Vaginal Cream USP, 0.01%) (Warner Chilcott)
- **Placebo:** Placebo (Test vehicle cream) Vaginal Cream (Prasco LLC)

10.4.3 Study Product Shipment, Storage, and Retention

[figure not shown]
[figure not shown]
The study product will be shipped to each Investigator's site from a central location. The Principal Investigator at each site is responsible for ensuring that all study products are stored in

CONFIDENTIAL PROTOCOL

A Randomized, Double-Blind, Placebo-Controlled, Parallel-Design, Multiple-Site Study to Evaluate the Therapeutic Equivalence of Estradiol Vaginal Cream, USP, 0.01% (Prasco LLC) to Estrace[®] Cream (Estradiol Vaginal Cream, USP, 0.01%) (Warner Chilcott) in the Treatment of Vulvar and Vaginal Atrophy, 71759501

[figure not shown]
locked, secure location, with access limited to the Investigator and his/her designee(s). An accurate inventory of the study product will be maintained in accordance with federal regulations.

Study product will be stored in a secure, locked location, at room temperature, protected from temperatures in excess of 40 °C (104 °F). Any excursions from the permitted temperature will require prompt notification to [REDACTED] and thereafter [REDACTED] will notify the Sponsor.

